#### 11 STATISTICAL METHODS

## 11.1 Sample Size Estimation

7244 healthcare workers will be enrolled in the trial outlined in this protocol, although data from this trial will be combined with the data from the 2834 participants enrolled into the first stage of this study which followed an identical protocol but where participants were randomised between BCG and no BCG which was given concurrently with the influenza vaccination, resulting in a total sample size of 10078 participants.

Participants will be randomly allocated in a 1:1 ratio to BCG vaccine group (n=3622, plus 1417 from the first stage who received influenza vaccine at time of randomisation), and to control (n=3622, plus 1417 from the first stage who received influenza vaccine at time of randomisation and no 0.9% NaCl placebo). This sample size was calculated based on the two primary outcomes of (1) symptomatic COVID-19 and (2) severe COVID-19. Since the study aims to assess two primary outcomes, an adjustment for multiplicity will be applied to maintain a global Type I error rate of 5% by splitting of this alpha.

For the primary outcome (1), symptomatic COVID-19 at 6 months: it is conservatively estimated that a proportion of 55% of subjects will be infected by symptomatic COVID-19 in the placebo group; applying a 1:1 ratio for randomisation, a total sample size of n=2016 (1008 group) will provide 95% power with 2-tailed 0.005 significance level (10% of the global significance level) for the Pearson chi-square test (with continuity correction) to detect an absolute difference of 10% between an incidence of symptomatic COVID-19 of 45% in the BCG vaccine group and 55% in the placebo group.

For the primary outcome (2), severe COVID-19 at 6 months, we powered the study to identify a risk ratio of 0.67 in the BCG compared with the placebo group for severe COVID-19 at 6 months (which is much more realistic than a risk ratio of 0.5 as per the original sample size). Assuming that 4% of subjects will be infected by severe COVID-19 by 6 months in the control group, a total sample size of n= 6076 (3038 per group) will provide 80% power with 2-tailed 0.04 significance level (80% of the global significance level) for the Pearson chi-square test to detect a risk ratio of 0.667, equivalent to an absolute difference of 1.3%. Note this calculation was conducted using an alpha of 0.04 to allow the remaining 0.01 to be spent on primary outcome (1) (alpha=0.005) and the interim analysis as originally planned (alpha=0.005, see section 11.4 for details of the interim analysis, total alpha for this outcome=0.045). Allowing for a 16% loss to follow up, it is planned that the study will recruit 7244 healthcare workers.

In the pre-planned meta-analysis, we will have a sample size of 10,078 participants (7244+2834), or 8062 participants allowing for an overall 20% loss to follow up. For the combined analysis it is expected that the drop-out will be slightly higher (20% instead of 16%) because it also includes participants recruited prior to the introduction of the placebo, i.e. not placebo controlled. Again assuming that 4% of subjects will be infected by severe COVID-19 by 6 months in the control group, a total sample size of n=8062 (4031 per group) will provide 90% power with 2-tailed 0.04 significance level for the Pearson chi-square test to detect a risk ratio of 0.667, equivalent to an absolute difference of 1.3%. This will be a secondary analysis of the final study report.

The original trial plan included a meta-analysis on all the outcomes (both COVID-19 and non-COVID-19 related outcomes) combining data from Stage 1 and Stage 2 participants. Stage 1 healthcare workers were recruited only in Victoria and Western Australia, both of which Australian states had almost negligible COVID-19 exposure risk during that trial period (30th Mar 2020 to 13th May 2020). In light of this, the overwhelming majority of Stage 1 blood samples are likely to be seronegative. Moreover, with a low prevalence of COVID-19, there is a high probability that positive SARS-CoV-2 serology results are false positive. For these reasons, in December 2021 the BRACE team has agreed that it is not justifiable to devote extra resources (time and costs) to the data cleaning of potential COVID-19 episodes and SARS-CoV-2 serology for all participants in Stage 1. As a consequence, the meta-analysis will

only be run on non-COVID-19 related outcomes and its main objective will be to determine if BCG vaccination compared with control reduces the rate and severity of febrile or respiratory illness over 12 months following randomisation in Stage 1 and Stage 2 healthcare workers.

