## 2.2. Background

Since the emergence of coronavirus disease 19 (COVID-19) in China in December 2019, there have been over 18,000,000 cases disease and greater than 690,000 deaths caused by the disease globally (as of August 2020). The causative agent of COVID-19 a novel coronavirus, severe acute respiratory syndrome-coronavirus 2 (SARS-CoV-2), has already spread to 108 countries (including over 200 cases in Australia) and it is predicted that up to 60% of the global population could become infected. Following from SARS in 2002 and Middle East respiratory syndrome (MERS) in 2012, SARS-CoV-2 is the third coronavirus to make the jump from animals to humans and emerge as a serious human pathogen in less than 20 years.

In approximately 80% of cases COVID-19 results in mild to moderate disease with symptoms similar to common respiratory diseases such as influenza-like illnesses, with fever in the majority (87.9%) of cases, followed by dry cough (67.7%), fatigue (38.1%), sputum production

(33.4%). In 14% of cases, SARS-CoV-2 causes severe disease requiring oxygen supplementation and/or mechanical ventilation, with a further 6% being critical cases that have respiratory failure, septic shock and/or organ failure.

There are worldwide efforts to reduce the peak of SARS-CoV-2 infection, in order to have enough hospital resources. However, with no vaccines or preventative interventions available to protect against COVID-19, current strategies rely on conventional control measures including travel restrictions, quarantines and increased hygiene practices. The overlap of COVID-19 symptoms with common respiratory diseases makes screening for SARS-CoV-2 infection difficult with diagnosis relying on microbiological confirmation of SARS-CoV-2 infection. Moreover, healthcare workers with these common respiratory symptoms are advised to be tested for SARS-CoV-2 infection prior to return to work. The loss of these healthcare workers with non-COVID-19 respiratory infections due to quarantine requirements places further pressure on the healthcare system during this critical time.

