## 3 TRIAL OBJECTIVES AND OUTCOMES

## 3.1 Objectives

Two primary outcomes have been chosen for this study: occurrence of symptomatic COVID-19 and occurrence of severe COVID-19. Considering the number of unknown factors and the little knowledge of this new virus, we deemed it of clinical importance to have sufficient power to detect the potential effect of BCG vaccine compared to control for both outcomes (occurrence of symptomatic COVID-19, as well as occurrence of severe COVID-19). Our hypothesis is that, compared to control, the BCG vaccine will reduce both the number of cases of COVID-19 (increase the number of asymptomatic SARS-CoV-2 infections) and the number of severe cases of COVID-19. In other words, we have the hypothesis that BCG vaccine would be able to shift the "severity of COVID-19" curve down, i.e. to generally reduce the severity of the symptoms in healthcare workers. Because of the potential for multiplicity testing, the method of controlling type I error is explained in the sample size section (11.1).

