## 6.1 Concealment mechanism

The control group will receive a placebo of 0.9% NaCl. Most people vaccinated with the BCG vaccine develop a papule/blister at the injection site around two-weeks after vaccination. Due to this, even using a placebo, it is not completely possible to blind participants to their treatment group allocation. The outcomes (symptomatic and severe COVID-19 or admission to hospital for COVID-19) are objective measures, it is however still plausible that participant's suspicion of their group allocation might bias the study results. This risk will be mitigated by using a placebo where an element of doubt over treatment allocation may persist even in the absence of scar formation. Members of the study team, except immunisers, will be blinded to the group allocation (by the removal of this variable and all other variables related to BCG from the dataset) until the formal detailed statistical analysis plan is confirmed and signed by all investigators and all data cleaning/preparation is complete.

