## 11.4 Interim Analyses

As part of the interim monitoring there will be a single formal interim analysis of the efficacy data. This interim analysis will be on a comparison of the number of cases of severe COVID-19 (primary outcome (2)) between the BGG group and the control group for those recruited post the introduction of the placebo (second stage of the study). The timing of the interim analysis will be event driven, and will be conducted using a time-to-event analysis, censoring participants who have not had the event at the time of their last follow-up. This data will be used to provide Kaplan-Meier estimates of the survival curve in the BCG and control groups, which will be used to estimate the proportion with severe COVID-19 at 6 months. These proportions will be used to compare the two groups.

The timing of the interim analysis will be determined by the original sample size calculation. Under the original sample size calculation, with 1668 per group and an incidence of 4% in severe COVID-19 at 6 months in the control group and 2% in the intervention group, this would equate to 67 + 33 = 100 cases in total. We therefore planned to conduct a formal interim analysis of severe COVID-19 once there had been 100 cases of severe COVID-19.

The stopping rule to be used in the interim analysis will be based on an alpha spending function, where the threshold to identify efficacy is based on the amount of data available at the time of the interim analysis relative to the data available at the end of the trial. The threshold for the interim analysis and the remaining alpha for the final analysis if the study is not stopped at the interim will be calculated using the Group Sequential Test (GST) of Two Proportions in NQuery (PTT12-1) with an alpha-spending function based on the Pocock stopping rule. This calculation will be based on an overall alpha of 0.045 for the primary

outcome (2), and the amount of available information at the time of the interim analysis (calculated as the percentage of participants with outcome data on severe COVID by 6 months relative to the final sample size).

This interim analysis of severe COVID-19 will be performed on all of the participants randomised into Stage 2 of the trial up to the interim analysis time point, comparing all the participants who are randomised to BCG and those randomised to placebo.

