A statistical analysis plan for the interim analysis will be written, shared with the DSMB and made publicly available prior to undertaking the interim analysis. This analysis plan will provide all the details of the interim analysis, including the threshold to be adopted for the interim analysis.

Given the dynamic nature of research in this field, the DSMB will be advised that this rule be used as a guideline rather than a formal rule, and should be interpreted in the context of external information and information on the efficacy of BCG vaccination on the incidence of symptomatic COVID-19.

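### Should symptomatic COVID-19 be tested at 0.05, not a fixed 0.005, once severe COVID-19 has succeeded?

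*Protocol*

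**What the plan says.** Protocol section 3.1 names two primary outcomes and states that "the method of controlling type I error is explained in the sample size section (11.1"). Section 11.1 then says that "an adjustment for multiplicity will be applied to maintain a global Type I error rate of 5% by splitting of this alpha". For symptomatic COVID-19 at 55% versus 45%, 1008 per group "will provide 95% power with 2-tailed 0.005 significance level (10% of the global significance level"). For severe COVID-19 at 4% with a risk ratio of 0.667, 3038 per group give 80% power at 0.04. A further 0.005 is set aside for the interim analysis, so severe COVID-19 has 0.045 in total.

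Section 11.4 confirms that total: "This calculation will be based on an overall alpha of 0.045 for the primary" outcome (2). The single interim efficacy analysis concerns severe COVID-19 only. The protocol states no testing order and does not pass alpha from one primary outcome to the other.

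**The concern.** A fixed split leaves alpha unused once one hypothesis has been rejected. If severe COVID-19 crosses its boundary, its 0.045 could be added to the 0.005 and symptomatic COVID-19 tested at 0.05, with the global error still at most 5%. A reader who sees the first-listed primary outcome held at one tenth of the global level may suspect that a real effect could be missed for no gain in error control.

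The protocol gives some reason to think that its planning values could fail. Section 11.1 weakened the severe effect to a risk ratio of 0.67, "which is much more realistic than a risk ratio of 0.5 as per the original sample size". Appendix 8 expects participants to receive COVID-19-specific vaccines during the trial. If symptomatic incidence or effect fell well short of plan, power at 0.005 would suffer while a more efficient rule was available.

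**Working it through.** **Step 1: is the split valid?** Section 11.1 allocates 0.005 (symptomatic) + 0.005 (interim, severe) + 0.04 (final, severe) = 0.05. Section 11.4 gives 0.045 for severe, and 0.005 + 0.045 = 0.05. By Bonferroni the chance of any false rejection is at most 5%, whatever the correlation between the outcomes.

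**Step 2: do the stated sample sizes reproduce?** Per group,

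n = [z(1−α/2)·√(2p̄(1−p̄)) + z(1−β)·√(p₁(1−p₁) + p₂(1−p₂))]² / (p₁−p₂)².

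- Symptomatic: p₁ = 0.55, p₂ = 0.45, z = 2.807 and 1.645. This gives (2.807 × 0.7071 + 1.645 × 0.7036)² / 0.01 = 987.3. The continuity correction, n/4·[1 + √(1 + 4/(n·0.10))]², gives 1007.2, so 1008. Matches.
- Severe: p₁ = 0.04, p₂ = 0.04 × 2/3, z = 2.054 and 0.842. This gives 3037.7, so 3038. Matches.
- Recruitment of 7244 with 16% loss leaves 7244 × 0.84 = 6085, against the 6076 required.

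**Step 3: what does 0.005 cost under the plan?** The trial is sized for severe COVID-19, so symptomatic COVID-19 also has 3038 per group. The standard error is √(0.495/3038) = 0.01276 and the expected z is 0.10/0.01276 = 7.83. The critical values are 2.81 at 0.005 and 1.96 at 0.05. Power exceeds 99.9% at both.

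**Step 4: how far can the plan slip?** With 3038 per group at 0.005, symptomatic power is still

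- 95% at 27% control incidence with the planned risk ratio of 0.818 (45/55), or at a risk ratio of 0.896 with 55% incidence;
- 80% at about 20% incidence, or at a risk ratio of 0.915.

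**Step 5: what would passing alpha on gain?** Assumptions, not protocol figures: interim at half the information, Pocock-type spending of 0.045 (severe power about 77% at 4% and risk ratio 0.667), severe cases nested in symptomatic ones, 4,000,000 simulated trials per scenario. The last two columns let severe incidence fall in proportion to symptomatic incidence, for example 4% × 20/55 = 1.45%.

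| Symptomatic control incidence, risk ratio | Power, fixed 0.005 | Passed on, severe held at 4% | Passed on, severe in proportion | Severe power, in proportion |
|---|---|---|---|---|
| 55%, 0.818 (plan) | >99.9% | >99.9% | >99.9% | 77% |
| 55%, 0.90 | 93% | 97% | 97% | 77% |
| 30%, 0.818 | 98% | 99% | 98% | 49% |
| 20%, 0.818 | 81% | 90% | 84% | 34% |
| 10%, 0.818 | 37% | 63% | 42% | 19% |
| 30%, 0.88 | 63% | 81% | 74% | 49% |

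Holding severe disease at 4% while symptomatic incidence falls from 55% to 10% means that severe cases rise from 4/55 = 7% to 4/10 = 40% of symptomatic cases. Alpha is released only if severe COVID-19 succeeds, so lower transmission that reduces both outcomes removes most of the benefit.

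**Step 6: what would it cost?** Under the fallback rule, any false rejection with both nulls true still needs severe to cross (at most 0.045) or symptomatic p ≤ 0.005, so the 5% limit holds. When severe COVID-19 truly responds and symptomatic COVID-19 does not, the symptomatic outcome's own error rises from 0.5% to 3.3–3.9% (severe risk ratio 0.667) or 4.8–5.0% (severe risk ratio 0.5).

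**The case for a change.** The best case for the fallback is that it has the same 5% familywise limit, can never reject less than the plain split, needs only two or three sentences and leaves sample size and interim boundaries alone. Section 3.1 makes 11.1 the home of type I error control, so the plain split is a choice the protocol itself fixes.

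The error bound and the arithmetic stand. So does a modest gain that does not depend on severe incidence: 93% to 97% at 55% incidence with a risk ratio of 0.90. But no passage assumes that effect, and none assumes symptomatic incidences of 10% to 40%. A risk ratio of 0.88 comes only from carrying the revision of the severe effect over to symptomatic disease: 1 − 0.182 × (0.333/0.5) = 0.88.

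The change would also not be free. Besides the error in Step 6, it would relax a primary outcome's level up to tenfold in a version dated 17 May 2022. Section 1.3 expected recruitment to end in March 2021, so on that timetable six-month follow-up was complete by about September 2021. Section 6.1 keeps the team other than immunisers blinded "until the formal detailed statistical analysis plan is confirmed and signed by all investigators and all data cleaning/preparation is complete", which would make a late change defensible, but its credibility would still be open to question. Success would also have to be defined by the test statistic, because under section 11.4 "the DSMB will be advised that this rule be used as a guideline rather than a formal rule". Finally, a testing order may properly be set in the SAP, which was not available for this review.

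**Conclusion.** The concern does not hold. The 0.005/0.045 split controls the global error at 5%, agrees between 11.1 and 11.4 in its total of 0.045 for severe COVID-19, and supports sample sizes that reproduce exactly. Under the protocol's own assumptions the stricter level costs no meaningful power: above 99.9% either way. Symptomatic power drops below the planned 95% only if incidence falls to about half of plan (27% against 55%) or the risk ratio weakens from 0.818 to about 0.90.

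Beyond those points a fallback would add power, but the amount rests on assumptions outside the document. At 20% incidence it is 81% to 90% if severe disease stays at 4%, and 81% to about 84% if it falls in proportion. Against this, the fixed split holds the symptomatic outcome's own error at 0.5%. Choosing between the two rules is a legitimate design preference, and the plain split needs no correction. The simulated figures assume 3038 per group, an interim at half the information and nested outcomes; the validity of the split and the power at 55% versus 45% do not depend on the interim timing or the nesting.

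### Section 11.1 claims 80% power for severe COVID-19 at a final alpha of 0.04, but the Pocock-type rule in 11.4 gives a smaller final alpha and about 76.5% to 79% power for an interim at 20% to 90% information

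*Protocol*

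**What the plan says.** Section 11.1 (Sample Size Estimation) plans severe COVID-19 at 6 months with a control risk of 4% and a risk ratio of 0.667. Of the 6076 evaluable participants, split equally between the arms, it says that they "will provide 80% power with 2-tailed 0.04 significance level (80% of the global significance level". With 16% loss to follow-up this becomes the recruitment target of 7244. On the alpha split it says: "Note this calculation was conducted using an alpha of 0.04 to allow the remaining 0.01 to be spent on primary outcome (1) (alpha=0.005". The other half of that 0.01 goes to the interim look at severe COVID-19, which 11.1 describes in these terms: "and the interim analysis as originally planned (alpha=0.005, see section 11.4 for details of the interim analysis, total alpha for this outcome=0.045". So 11.1 has 0.005 for symptomatic COVID-19, 0.005 for the interim on severe COVID-19 and 0.04 for the final test of severe COVID-19.

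Section 11.4 (Interim Analyses), to which 11.1 refers, describes a different arrangement. The interim threshold is found by a group sequential calculation for two proportions "with an alpha-spending function based on the Pocock stopping rule", applied to an overall 0.045. It says that "the remaining alpha for the final analysis if the study is not stopped at the interim will be calculated" by the same run. Information is "calculated as the percentage of participants with outcome data on severe COVID by 6 months relative to the final sample size". The interim is triggered by 100 severe cases, a number taken from the original sample size of 1668 per group. No interim level of 0.005 and no final level of 0.04 appears in 11.4.

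**The concern.** The two sections agree on the total of 0.045 for severe COVID-19 but not on how it is divided. Section 11.1 gives almost all of it to the final analysis. A Pocock-type function spends heavily at the interim, so the final level must be well below 0.04 unless the interim comes very early. The 80% in 11.1 was calculated for the former split and was not recalculated for the latter.

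Severe COVID-19 is the outcome that sets the recruitment target, so this is the power figure readers will rely on. Two misreadings follow. A reader of 11.1 would expect a final test at 0.04, whereas under 11.4 with a mid-trial interim a final p-value between about 0.025 and 0.04 is not significant. A non-significant result would also be judged against a power that the design does not have.

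**Working it through.** **Inputs.** From 11.1: control risk 4%, risk ratio 0.667 (taken as 2/3, so 2.667% on BCG), 3038 per group, final two-sided alpha 0.04, interim alpha 0.005, total 0.045. From 11.4: one interim, Pocock-type spending of 0.045, a trigger of 100 severe cases, and 1668 per group in the original calculation. The information fraction t is not given and is treated as an assumption.

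**1. Reproduce the stated figure.** Chi-square test with pooled variance under the null and no continuity correction, mean risk 0.03333:

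n = [z(0.98)·√(2 × 0.03333 × 0.96667) + z(0.80)·√(0.04 × 0.96 + 0.02667 × 0.97333)]² / 0.01333² = 3037.7

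This rounds up to 3038 per group, with power 80.0%. The figure is right for a single test at 0.04. With the 0.005/0.04 split added, overall power is still 80.0% to 80.3% for t from 0.2 to 0.9, so 80% was also right for the old interim plan.

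**2. Apply the rule in 11.4.**

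- Interim level: a₁ = 0.045 × ln(1 + (e − 1)t).
- Final level: the critical value is solved so that total two-sided error is 0.045, using a bivariate normal with correlation √t.
- Drift at full information: 0.01333 × √3038 / √(0.0384 + 0.02596) = 2.897. At the interim it is 2.897√t.
- Overall power: the probability of crossing at either look.

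Example at t = 0.49: a₁ = 0.045 × ln(1.842) = 0.0275 (critical value 2.205). The final critical value is 2.242, a level of 0.0249. Overall power is 76.6%.

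| t | Interim level | Final level | Overall power |
|---|---|---|---|
| 0.1 | 0.0071 | 0.0387 | 79.9% |
| 0.2 | 0.0133 | 0.0339 | 78.7% |
| 0.3 | 0.0187 | 0.0302 | 77.7% |
| 0.4 | 0.0235 | 0.0271 | 77.0% |
| 0.49 | 0.0275 | 0.0249 | 76.6% |
| 0.55 | 0.0299 | 0.0237 | 76.5% |
| 0.6 | 0.0319 | 0.0229 | 76.5% |
| 0.7 | 0.0355 | 0.0216 | 76.8% |
| 0.8 | 0.0389 | 0.0211 | 77.5% |
| 0.9 | 0.0421 | 0.0222 | 78.9% |

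Using pooled variance in the drift changes power by less than 0.1 point.

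**3. Where would the 11.1 split arise?** The interim spend equals 0.005 at t = 0.068. The final level equals 0.04 at t = 0.077, and 0.0772 × 6076 = 469 participants with 6-month data.

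**4. Which fraction is plausible?**

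- Trigger: if the 100 cases come from participants with complete follow-up at the planning rates, 100 / 0.03333 = 3000 participants, and 3000 / 6076 = 0.49.
- Original sample size: 2 × 1668 = 3336, and 3336 / 6076 = 0.55.

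Power is close to its minimum at both values.

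**The case against.** The strongest reply is that 11.1 only records how 6076 was derived. It describes the interim as the one planned originally and sends the reader to 11.4, and both sections give 0.045. That shows where the number came from but does not correct it: 11.1 still says, as current text, that this sample size will give 80% power at 0.04, and 11.4 gives no replacement.

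The second point is that the information fraction is unknown. The interim is event-driven and censors at last follow-up, so the fraction with 6-month data could be well below 0.49. At the extremes the gap closes: about 80.6% at t = 0.05, 80.0% at 0.95 and 81.1% at 0.99. With no interim at all, the full 0.045 gives 81.4%. The wording of the rule could also be read as constant Pocock boundaries, which give 75.1% to 80.3% for t from 0.2 to 0.9. All of this stands, so the result has to be a range conditional on t. The text does specify a spending function, and under it power is below 80% throughout 0.2 to 0.9.

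Third, 11.4 promises a separate public analysis plan for the interim, with the threshold. Leaving the threshold there is acceptable. The fault is in what the protocol does state. Likewise, 11.4 asks the DSMB to treat the rule as a guideline, but that concerns stopping. The final level is still what remains after the spend.

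Finally, the loss is small beside the other planning uncertainty. At t = 0.6 a control risk of about 4.3%, or about 9% loss instead of 16%, would restore 80%, while a control risk of 3.5% would cost about 6 points with no interim. This version is dated May 2022, after the expected end of recruitment in March 2021, so a restated power cannot change enrolment. That is fair. It limits the remedy to a correction of the text.

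**Conclusion.** The concern holds. The 80% and the 0.04 in 11.1 belong to an interim plan that 11.4 has replaced. Under the current rule, overall power with 3038 per group is 76.5% to 78.9% for information fractions of 0.2 to 0.9, a shortfall of about 1 to 3.5 points. The final level is 0.021 to 0.034. At the fraction implied by the 100-case trigger (0.49) the final level is 0.0249 and power 76.6%.

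This rests on the planning risks in 11.1, the standard Pocock-type spending function, and an assumed fraction, since the protocol fixes none. For an interim near 10% information the gap almost disappears. Type I error is not affected: 0.045 is held for this outcome and 0.005 for symptomatic COVID-19. The loss of power is modest. The larger discrepancy is in the final significance level, about 0.025 at mid-trial against a stated 0.04, for a primary outcome.

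**What to change.** Leave the spending rule in 11.4 unchanged as the only rule that sets the levels. In 11.1, delete the 0.04/0.005 split or mark it as superseded, and replace the power sentence with:

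> Severe COVID-19 has an overall two-sided alpha of 0.045, divided between the interim and final analyses by the spending function in section 11.4. At an information fraction of [x] (participants with 6-month outcome data / 6076), the interim level is [a1], the final level is [a2] and overall power with 3038 per group (4% versus 2.67%) is [p].

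If the interim has been held, enter the actual fraction. Otherwise enter the expected fraction and a range. At x = 0.49 the entries are 0.0275, 0.0249 and 76.6%.

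The cost is two sentences and one run of the calculation that 11.4 already specifies. The decision rule stays the same and no participants are added. The price is a stated power about 1 to 3.5 points lower.
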